7. RATIONALE AND BACKGROUND

Stroke is the leading cause of mortality and disability among adults in China, which is characterized by high morbidity, disability and mortality. With the aging of society, the acceleration of urbanization, and popular unhealthy lifestyle among residents, the stroke burden in China displayed an explosive growth trend and elderly patients with AIS are becoming common in China. [\[R19-3903\]](#), [\[R21-1796\]](#), [\[P21-04631\]](#) According to the 2018 data in Chinese acute ischaemic stroke (AIS) patients, it was deduced that there were 12.42 million Chinese AIS patients and 1.96 million patients died due to AIS. [\[R19-3903\]](#) Therefore, the prevention and treatment of stroke is still facing huge challenges in China, further strengthening the prevention and treatment system and improving the prognosis of stroke patients are urgent needs in stroke management.

The benefit of intravenous thrombolysis (IVT) treatment within 4.5 hours of symptom onset for AIS patients has been well proven and recommended by international/national guidelines. [\[P19-10385\]](#), [\[P21-02289\]](#), [\[P19-10855\]](#) A meta-analysis of randomised controlled trials demonstrated a positive benefit-risk ratio for alteplase when used according to label criteria. [\[P20-06029\]](#) The benefit-risk ratio changed with time to treatment: earlier treatment was associated with better outcomes, while delayed treatment was associated with reduced benefit.

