1.1 Does the protocol specify timelines for				
1.1.1 Start of data collection ¹				6
1.1.2 End of data collection ²				6
1.1.3 Progress report(s)				NA
1.1.4 Interim report(s)				NA
1.1.5 Registration in the EU PAS Register®				6
1.1.6 Final report of study results.				6

Comments:

--

5. Section 2: Research question	Yes	No	N/A	Section Number
2.1 Does the formulation of the research question and objectives clearly explain:				7 and 8
2.1.1 Why the study is conducted? (e.g. to address an important public health concern, a risk identified in the risk management plan, an emerging safety issue)				7
2.1.2 The objective(s) of the study?				8
2.1.3 The target population? (i.e. population or subgroup to whom the study results are intended to be generalised)				9.2.2
2.1.4 Which hypothesis(-es) is (are) to be tested?				NA
2.1.5 If applicable, that there is no a priori hypothesis?				NA

Comments:

--

¹ Date from which information on the first study is first recorded in the study dataset or, in the case of secondary use of data, the date from which data extraction starts.

² Date from which the analytical dataset is completely available.

6. Section 3: Study design	Yes	No	N/A	Section Number
3.1 Is the study design described? (e.g. cohort, case-control, cross-sectional, other design)				9.1

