7. RESEARCH METHODS

7.1 STUDY DESIGN

This study is a non-interventional study (NIS) based on existing data. We will analyse data of AIS patients aged ≥ 18 years in China collected from the ZSQCC platform. [\[P21-04780\]](#), [\[P21-04783\]](#), [\[P21-04784\]](#), [\[P21-04779\]](#), [\[P21-04782\]](#)

Approximately 11700 AIS patients in total are recorded in the ZSQCC platform and will be analysed in this study. There were approximately 8500 AIS patients (≥ 18 years of age) who were treated with IV rt PA and 3200 patients who were admitted to the hospital within 4.5 hours of symptom onset and did not receive reperfusion treatment from Jan 2017 to Mar 2020. In the China National Stroke Registry I (2007-2008), the 12-month mortality rate for post-stroke patients was approximately 14%. [\[R21-1852\]](#) For this study, it is assumed that 1-year mortality is 12% and 15% for the rt-PA treatment cohort and the cohort who did not receive reperfusion, respectively. In total, 6069 patients with a treatment ratio 2:1 are needed to observe 855 events and to detect the difference (hazard ratio=0.79) with a 2-sided alpha of 0.05 and 90% power. In addition, considering a treatment ratio 1:1 with the same assumption described above with power of 90% at a 2-sided, 5% significant level, roughly 5400 patients are needed to observe 756 events to detect the difference.

[figure not shown]
Patients meeting the inclusion and exclusion criteria will be divided into 2 cohorts:

- IV rt-PA cohort: Patients who received IV rt-PA within 4.5 hours of symptom onset
- Non-reperfusion cohort: Patients who arrived or were admitted to the hospital within 4.5 hours of symptom onset and did not receive any reperfusion treatment

Propensity score matching (PSM) will be used to match the baseline characteristics between the above 2 cohorts. The primary, secondary outcomes, as well as baseline characteristics will be compared between the matched cohorts.

The flow of data selection for each of the 2 reporting patient cohorts is depicted in Figure 1 below.

Figure 1 Patient cohorts selected for the non-interventional study

Note: dotted lines: excluded

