7.3 STUDY POPULATION

No sampling will be undertaken and all patients who meet all the inclusion criteria and none of the exclusion criteria will be included.

The inclusion and exclusion criteria are listed below:

Inclusion criteria:

- Patients registered in the ZSQCC platform from Jan 2017 to Mar 2020
- ≥ 18 years of age
- Diagnosed with AIS at admission
- Arrived or admitted to the hospital within 4.5 hours of symptom onset
- If treated with IV rt-PA: received IV rt-PA within 4.5 hours of symptom onset

Exclusion criteria:

- Documented IVT contraindication except age to IV rt-PA treatment according to the SmPC
- Missing any one of the key data (age, gender, baseline National Institutes of Health Stroke Scale [NIHSS], time of symptom onset, time of hospital arrival or admission, IVT or not, time of IV rt-PA treatment)
- Received thrombolysis agents other than rt-PA (urokinase, tenecteplase, recombinant plasminogen activator, prourokinase, streptokinase)
- Received endovascular treatment
- Received IV rt-PA after 4.5 hours of symptom onset

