To account for potential confounding, the 2 cohorts will be 1:1 or 2:1 matched by baseline characteristics using the Propensity Score Matching method. The feasibility of PSM will be evaluated based on available sample size and descriptive results. If patient characteristics between the 2 cohorts are significantly different, i.e., less than 50% of patients in the IV rt PA cohort can be matched to the non-reperfusion cohort based on PSM, the study design will be re-evaluated before proceeding to analysis. The PSM aims to balance the 2 cohorts on baseline covariates. The propensity score model will include age, gender, baseline NIHSS/NIHSS categories (0-4, 5-10, 11-15, 16-21, and ≥ 22), pre-stroke mRS, medical insurance status, smoking status, hospital level, diabetes, coronary artery disease, atrial fibrillation, prior stroke/transient ischaemic attack, hypertension, anti-platelet, lipid lowering, oral anticoagulation, and time from symptom onset to hospital admission. The method of Nearest Neighbour matching will be used (a maximum caliper width equal to 0.2 of the standard deviation of the logit of the propensity score) to select the matched samples. Then we will compare the baseline characteristics of the 2 propensity-score-matched cohorts. The absolute standardized difference (ASD) between the 2 PS-matched cohorts will be calculated, where at least 0.1 ASD will be considered a significant difference. For baseline covariates that are not sufficiently balanced after PSM, they will be included in an appropriate multivariate model to adjust for those differences.

For the primary outcome, a comparison of the percentage of 1-year* all-cause mortality (mRS=6) between the 2 matched cohorts will be conducted using a Chi-square test. A Kaplan-Meier curve with log-rank test will be used to analyse the data. Cox regression models will be used to estimate hazard ratios (95% confidence interval) between the 2 matched cohorts.

For the secondary outcomes, descriptive summaries will be conducted in the PS-matched cohorts separately. For the categorical variables including functional independence (mRS 0-2), favourable clinical outcome (mRS 0-1), and mRS 5-6 at 1 year, the Chi-square test and conditional logistic regression model will be conducted. For the distribution of mRS score at 1 year, the Wilcoxon rank sum test and ordinal logistic regression model will be performed to calculate the odds ratio and 95% CI.

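### The matched hazard ratio can cover at most 75% of rt-PA patients at 2:1 (38% at 1:1), yet nothing in the plan ties the conclusion to the patients kept

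*SAP*

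**What the plan says.** Protocol section 8 and SAP section 6 set out to compare 1-year mortality in AIS patients given IV rt-PA within 4.5 hours with that in early arrivals given no reperfusion. Neither restricts the rt-PA group to a subset.

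On who is studied, SAP 7.3 says: "No sampling will be undertaken and all patients who meet all the inclusion criteria and none of the exclusion criteria will be included". The Protocol's section on study population (9 B ii) agrees. In the ENCePP checklist (Protocol Annex 2), item 2.1.3 asks about "The target population? (i.e. population or subgroup to whom the study results are intended to be generalised". It is answered yes, with a pointer to section 9.2.2, the study population.

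SAP 7.1 gives the numbers: "Approximately 11700 AIS patients in total are recorded in the ZSQCC platform and will be analysed in this study". On the treated side it says: "There were approximately 8500 AIS patients (≥ 18 years of age) who were treated with IV rt PA". The remaining 3200 or so are the early arrivals without reperfusion.

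On the analysis, SAP 11.1 plans nearest-neighbour propensity matching, 1:1 or 2:1, with a caliper of 0.2 SD of the logit score. It then says: "Cox regression models will be used to estimate hazard ratios (95% confidence interval) between the 2 matched cohorts". The secondary outcomes are also analysed in the matched cohorts. Balance is judged by the absolute standardised difference (ASD) between the two cohorts, with a limit of 0.1. If fewer than 50% of rt-PA patients can be matched, the design is to be re-evaluated before analysis (Protocol 9 G i; SAP 11.1).

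**The concern.** Matching usually draws from a larger pool of controls and keeps nearly all treated patients. Here the treated cohort is the larger one, so treated patients are discarded. Those kept are the ones whose propensity scores lie close to those of untreated patients.

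The balance check cannot show this. It compares matched rt-PA patients with matched controls, and it can be perfect while matched rt-PA patients differ clearly from all rt-PA patients. The Protocol's limitations (9 I) discuss whether Zhejiang represents China, not the loss of rt-PA patients through matching.

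This matters if the effect varies with factors that drive treatment. The Protocol's background says of time to treatment that "earlier treatment was associated with better outcomes, while delayed treatment was associated with reduced benefit". Onset-to-hospital time, NIHSS and age are all in the propensity model. If the effect varies with them, the matched hazard ratio is not the hazard ratio in rt-PA-treated patients, and it also differs between the 1:1 and 2:1 options. The report could then attribute to rt-PA patients in general an effect estimated in a selected part of them.

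**Working it through.** **Inputs.** SAP 7.1: 8500 rt-PA patients, 3200 controls, HR 0.79, two-sided alpha 0.05, power 90%. SAP 11.1: ratio 1:1 or 2:1, the 50% rule, ASD limit 0.1. Assumed: each control is used once, and 2:1 means two rt-PA patients per control.

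**The plan's own sample size.** Events = (1.960 + 1.282)² / [p(1 − p)(ln 0.79)²].
- 1:1 (p = 1/2): 757 events, against 756 stated. 757/0.14 = 5407 patients, against about 5400.
- 2:1 (p = 2/3): 851 events, against 855 stated. 851/0.14 = 6079 patients, against 6069.

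The 14% is the plan's implied overall event rate (756/5400). The stated sizes are reproduced.

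**The assumed reading of 2:1.** The reverse reading would need 6069 × 2/3 = 4046 controls, more than the 3200 available. It would also lower the ceiling to 1600/8500 = 18.8%.

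**Ceiling on the share of rt-PA patients.** Share ≤ ratio × 3200/8500.
- 1:1: 3200/8500 = 37.6%, so at least 8500 − 3200 = 5300 are left out.
- 2:1: 6400/8500 = 75.3%, so at least 8500 − 6400 = 2100 are left out.
- 2:1 with 90%, 80% or 70% of controls matched: 67.8%, 60.2% or 52.7%.

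**The 50% rule.** It needs 8500/2 = 4250 matched rt-PA patients.
- 1:1 can supply at most 3200, so the rule is always triggered.
- 2:1 needs 4250/2 = 2125 complete sets, or 2125/3200 = 66.4% of controls. It can therefore pass with half of the rt-PA cohort absent. The planned minimum of 6069 includes 4046 rt-PA patients (47.6%), just below the rule.

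**How different the kept patients may be.** This needs assumptions. In simulated cohorts of 8500 and 3200, NIHSS, age and onset-to-arrival time drove treatment, with an assumed propensity AUC of 0.63 to 0.75, caliper 0.2 SD and controls as the index group. At 2:1, 56% to 69% of rt-PA patients were matched. They differed from all rt-PA patients by an ASD of 0.18 to 0.33. A second simulation (AUC 0.62 to 0.73) gave 58% to 69% and 0.14 to 0.34. Both ranges exceed 0.1.

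**Effect on the hazard ratio at 2:1.** The assumed gradient runs from HR 0.65 at 1 SD early to 0.96 at 1 SD late. The hazard ratio was then 0.806 to 0.812 in all rt-PA patients and 0.835 to 0.838 in the 2:1 set.
- ln(0.835/0.806) = 0.035, and ln(0.838/0.812) = 0.032.
- |ln 0.79| = 0.236, so the shift is 0.032/0.236 = 13% to 0.035/0.236 = 15% of the planned effect.

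These figures pair lower end with lower and upper with upper. With no variation in effect the shift is negligible.

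**The case against.** The strongest reply has five parts.

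- **The plan has a safeguard.** The 50% rule means that a 1:1 analysis cannot simply proceed. This stands. A reader might infer that the study will report a hazard ratio from little more than a third of its rt-PA patients; the documents do not support that without a re-evaluation first. The rule remains a feasibility check. It names no target and places no limit on wording.
- **No sentence states the target.** A reader might infer that the plan declares all eligible patients as its target and then contradicts itself. That is too strong. The target is inferred from the objectives and from a checklist pointer, and SAP 7.1 says openly that the matched cohorts are compared. What is missing is a statement of whom the estimate describes.
- **The gradient is assumed.** This stands. The background passage speaks of benefit-risk and outcomes, not of a mortality hazard ratio. The same section says that randomised studies showed no effect on 3-month mortality. Its only mortality figures by timing are HR 0.63 (0.48 to 0.82) overall and 0.58 (0.40 to 0.82) for arrival within 3 hours, with widely overlapping intervals. The direction of any shift also depends on the gradient. The documents therefore do not show that the matched hazard ratio is materially wrong.
- **The shift is small.** At 2:1 it is under half of the standard error of about 0.08 seen in the 1:1 simulation. This is true, but a systematic shift does not show in a confidence interval.
- **Part is already planned.** Baseline tables before and after matching allow the comparison by eye, and the SAP lists subgroups by NIHSS, age and onset-to-treatment time without a size threshold. The Protocol does set one (5400 or 6069 per subgroup), against a matched set of at most 6400 (1:1) or 9600 (2:1) patients, so few subgroups could qualify under it.

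**Conclusion.** The point holds as one of interpretation and reporting. It does not show that the matched analysis is invalid.

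The document figures alone give the firm part. With each control used once, at least 2100 of 8500 rt-PA patients (25%) cannot enter the 2:1 hazard ratio, and up to half may be absent without triggering the 50% rule. No planned balance criterion or limitation covers this, and no effect estimate uses the full eligible population. Reuse of controls, which the SAP neither states nor excludes, could raise the share. The planned sizes of 5400 and 6069 are counts of patients, which fits use without replacement.

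The size of any distortion is conditional. It is 13% to 15% of the planned log effect at 2:1 under a strong assumed gradient, less with a weaker one, and negligible if the effect is constant. The correction is worth making because it is cheap and settles which patients the primary conclusion describes.

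**What to change.** In SAP 11.1:

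1. Report the number and percentage of rt-PA patients matched. Add to the planned before-and-after tables the ASD of matched versus all eligible rt-PA patients.
2. If that ASD is 0.1 or more for a key variable (NIHSS, age, pre-stroke mRS or onset-to-hospital time), word the primary conclusion for the matched patients, not for rt-PA-treated AIS patients in general.
3. Pre-specify one supplementary Cox analysis of all eligible patients, weighted to the rt-PA cohort with the same propensity score: weight 1 for rt-PA, PS/(1 − PS) for controls, robust standard error. State a truncation rule, and report the largest weights and the effective sample size. Show the result beside the matched hazard ratio, which stays primary.

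The cost is one table column and one model on existing data. The weighted interval may be wider: the simulated standard error was about 0.07 to 0.11, against 0.08 for 1:1 matching. It may also lean on a few high-score controls, since untruncated weights in simulated cohorts reached 6 to 14 times the mean. The conclusion may end up narrower than hoped.

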11.2 SAFETY ANALYSIS

This study is a NIS based on existing data. From safety information collecting and reporting perspective, this study will not involve individual medical record review, thus no adverse event/adverse drug reaction information is required to collect. The analysis refers to Section 10.1.

Proprietary confidential information © 2021 Boehringer Ingelheim International GmbH or one or more of its affiliated companies

12. QUALITY CONTROL

The statistical analytic approach and programming code will be reviewed/repeated by a second analyst.

ANNEX 1. ADDITIONAL INFORMATION

None

